#### 5.2.5 – Expected duration of participation for each subject

Each patient is expected to participate in the study for up to 16 months (cf. Table 8).

The patient's participation in the study begins when patient is determined eligible to participate and he/she has signed the consent form, after having received the appropriate and mandatory information about the study.

The patient's participation in the study ends if any of the situations described in section 5.2.3 – Criteria and procedures for withdrawal or termination of a subject's participation occurs.

#### 5.2.6 – Number of subjects required to be included in the clinical investigation

The number of subjects to be included is 374 patients, i.e. 187 patients in each group (cf. 6.2 – Sample size). The maximum number of subjects to be included in the United States is 80.

#### 5.2.7 – Estimated time required to include this number (i.e. the period of enrollment)

The estimated enrollment period is 22 months.

In case of significant changes in the inclusion phase duration, the relevant Ethics Committees, IRBs, and regulatory Health Authorities, as well as all concerned investigators, will be promptly notified.

At any time, the sponsor may interrupt or suspend enrollment of patients in the study for clinical/safety reasons (such as if an unanticipated adverse effect is observed or suspected) related to the device under investigation. In that case, the relevant Ethics Committees, IRBs, and regulatory Health Authorities, as well as all concerned investigators, will be promptly notified.

In addition to the sponsor, any Ethics Committee, IRBs, or regulatory Health Authorities may also interrupt or suspend enrollment of patients in the study for clinical/safety reasons related to the devices under investigation.

### 5.3 – Study procedures

#### 5.3.1 – Screening and enrollment

Patients must be informed about the investigation and the potential benefits and risks of the study prior to enrollment. Only those patients who voluntarily provide written consent to participate will be eligible for enrollment.

The following procedures must be conducted **before** inclusion of the patient in the study:

- Evaluate the patient to determine conformance with the inclusion and exclusion criteria. Source data that demonstrate conformance with inclusion criteria should be retained at the investigational site.
- Obtain written informed consent.

Patients are considered enrolled into this clinical study once they have signed an informed consent and met all eligibility criteria. Patients who do not sign an informed consent or do not meet eligibility criteria upon further testing are not eligible and should not be enrolled in the trial.

 <small>ARTIFICIAL INTELLIGENCE SERVING HEART DISEASE</small>	CLIPL-01-002-E	CONFIDENTIAL
	CLINICAL INVESTIGATION PLAN	F 09 XX 01 Rev.A

**After** having obtained the informed consent from the patient (and before ablation):

- Fill-out enrollment in appropriate eCRF
- Obtain and record the following data in appropriate eCRF:
  - Patient's demographics
  - Mandatory documentation of the maximum sustained AF duration or number of cardioversions (ECG/physician's letter)
  - Current vitals (physical examination, 12-lead ECG)
  - Routine clinical data including type of AF, LA diameter/surface (echo) or volume (scanner), CHA2DS2-VASC score, comorbidities, etc.
  - Patient's current medications
- Provide the patient with Quality-Of-Life questionnaires (SF-36 and AFEQT) and report answers in appropriate eCRF
- For US subjects: A TEE screening will be performed within 48 hours of the ablation procedure unless data from a TEE performed prior to enrollment is available and the TEE was performed within 48 hours of the ablation procedure.
  - If a patient cannot undergo TEE, the use of intracardiac echocardiography at the start of the ablation procedure to exclude LA thrombus is acceptable.

#### 5.3.2 – Randomization

After successful enrollment, the patient will be automatically randomized to one of two arms through the eCRF system: “Anatomical” arm (PVI) or “Tailored” arm (Dispersion + Tailored-PVI). In Europe, randomization will be stratified in order to balance the treatment arms in terms of patients with persistent AF (< 12 months) and long-standing persistent AF (≥ 12 months).

Subjects will not be informed of their randomization assignment.

#### 5.3.3 – Pre-ablation Medication

Treatment with antiarrhythmic medications should be stopped before ablation.

Continuous anticoagulation with warfarin (INR 2-3) or NOAC for > 4 weeks prior to ablation is mandatory. Anticoagulation should not be interrupted before the ablation procedure, unless specifically instructed by the investigator. Only 1 or 2 doses of oral anticoagulation may be interrupted by the investigator.

#### 5.3.4 – Index procedure

The subject will be scheduled to undergo study treatment after the subject has met all inclusion and exclusion criteria, has signed the study informed consent form, has completed the baseline assessments and has been randomized.

#### AF induction

If the patient does not present in spontaneous sustained AF at the beginning of the procedure, sustained AF must be induced by atrial burst pacing, either with or without the additional infusion/injection of isoproterenol (20 microg/min) ± adenosine (according to site practice).

In the Tailored group, should AF not be inducible or be inducible and non-sustained, the patient will undergo conventional AF ablation per physician discretion. This patient/case will not be considered in the per-protocol analysis.

 <small>ARTIFICIAL INTELLIGENCE SERVING HEART DISEASE</small>	CLIPL-01-002-E	CONFIDENTIAL
	CLINICAL INVESTIGATION PLAN	F 09 XX 01 Rev.A

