### Mapping (only for Tailored group)

For the Tailored group, careful biatrial high density dispersion mapping must be performed as the first step of the procedure. A biatrial mapping shorter than 20 minutes is considered incomplete. An incomplete mapping with failure to terminate the AF is considered a deviation of the protocol (cf. X – DEVIATIONS FROM CLINICAL INVESTIGATION PLAN).

Operators must map each region of both atria carefully. Electroanatomic color maps (i.e. voltage maps with minimal interpolation area) or the density of electroanatomic dots on 3D shells can be visually used to verify that the biatrial mapping has been completed. Operators must insist in difficult areas: ridge, anterior Right Superior Pulmonary Vein, area around the transseptal puncture, CS, right septum, area between RA Appendage (RAA) and septum.

Operators should move the mapping catheter slowly and remain in each position for at least 2-3 seconds. If the upper frame of VX1 interface changes from blue to orange/red, the corresponding dipoles must be manually tagged on the 3D shells (white/golden dots respectively – cf. VX1 instructions-for-use). Accuracy and relevance of dispersion regions should be confirmed by the operator by checking EGMs visually. If VX1 identifies an area of dispersed electrograms that the operator does not agree with, this should be documented.

If a dispersion area is detected, the operator must stay and move slowly in this area: a high number of dots is required to define the precise boundaries of the dispersion area.

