#### Ablation procedure in the Anatomical group

In the Anatomical group, the procedure endpoint is isolation of all four PVs, documented according to each site routine practice (e.g. bidirectional block with mapping catheter).

The operator creates a contiguous circular lesion around each pulmonary vein antrum (1-2 cm from the ostia) with point-by-point applications of RF energy. If the patient is not converted to sinus rhythm at the end of the procedure, a DC electrical cardioversion must be performed.

No RF applications outside the PV antra are allowed (cf. Figure 6 (b)). RF applications at the carinas are allowed (cf. Figure 6 (a)).

[figure not shown]

Figure 6: RF applications (a) allowed at the carinas and (b) forbidden outside PV antra

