## **VI – STATISTICAL CONSIDERATIONS**

### **6.1 – Design, statistical methodology and analytical procedures**

Standard summary statistics will be calculated for all study variables (demographics and outcomes) by study group and for all patients. For continuous variables, statistics will include means, standard deviation and 95% confidence intervals for means when assumptions of normal distribution are not violated. Median and quartiles may also be presented. Categorical variables will be summarized using frequency distributions.

The analysis for the primary endpoint will be a modified Intention-To-Treat (mITT) analysis, allowing exclusion of some randomized subjects in a justified way:

- Patients that are deemed ineligible after randomization or that do not have any AF ablation will be excluded
- Patients in the Tailored group for whom AF cannot be induced and who undergo conventional ablation will be included in this analysis
- Patients lost to follow-up (death, disability, relocation, or drop-out) during the 3-month blanking period will be excluded
- Patients who complete at least their 3-month follow-up but who are lost to follow-up (death, disability, relocation, or drop-out) before the 12-month follow-up will be included in the analysis and the data will be censored
- Patients who undergo a 3rd ablation procedure (re-repeat procedure) will be included in the analysis but the data will be censored at the time of the 3rd procedure.

A per-protocol (PP) population will also be evaluated and will serve as supportive analyses to the mITT analysis. In the PP analysis, the population will be analyzed according to the treatment actually received at the start of the study, and will consist of patients that met all the inclusion criteria, none of the exclusion criteria, were successfully treated, had no important protocol deviations and attended all the scheduled follow-up visits.

 <small>ARTIFICIAL INTELLIGENCE SERVING HEART DISEASE</small>	CLIPL-01-002-E	CONFIDENTIAL
	CLINICAL INVESTIGATION PLAN	F 09 XX 01 Rev.A Page 33/47

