4.2.4 Sensitivity Analyses of Primary Endpoint

The Primary Endpoint Analysis will additionally be conducted in the PP population.

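### Failed AF induction removes patients from the per-protocol set in the Tailored arm only, which leaves the supportive comparison open to selection bias

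*Protocol*

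**What the plan says.** The AF induction paragraph of Protocol 5.3.4 opens with a requirement that names no arm: "If the patient does not present in spontaneous sustained AF at the beginning of the procedure, sustained AF must be induced". The next heading, on mapping, is expressly limited to the Tailored group; the induction heading is not.

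The consequence of failed induction is written for one arm: "In the Tailored group, should AF not be inducible or be inducible and non-sustained, the patient will undergo conventional AF ablation per physician discretion". The paragraph then ends: "This patient/case will not be considered in the per-protocol analysis".

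For the Anatomical arm, "the procedure endpoint is isolation of all four PVs", which does not depend on AF being present.

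On analysis sets, Protocol 6.1 says that in the per-protocol (PP) analysis "the population will be analyzed according to the treatment actually received at the start of the study". SAP 4.1.3 keeps that principle and adds eligibility, a successful index procedure, no important deviations and follow-up compliance. It does not mention inducibility. SAP section 3 gives the SAP precedence over the protocol. Protocol 6.1 and SAP 4.1.2 both keep non-inducible Tailored patients in the mITT set. SAP 4.2.4 names one sensitivity analysis of the primary endpoint: "The Primary Endpoint Analysis will additionally be conducted in the PP population". SAP 4.3.2 does the same for the first two secondary endpoints.

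**The concern.** Eligibility does not require the patient to be in AF on the day of ablation, and 5.3.4 provides for patients who are not. Whether AF can then be induced and sustained is known before any ablation and is a feature of the patient, not an effect of the assigned strategy. Removing such patients from one arm changes that arm's case mix and leaves the other as randomised.

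If their AF recurrence risk differs from that of other patients, the PP comparison moves without any treatment effect. PP is the only sensitivity population named for the primary endpoint. Agreement or disagreement between PP and mITT would then partly reflect this filter, and could be mistaken for evidence on robustness.

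**Working it through.** **Step 1. Does any other rule remove the Anatomical patient?**

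| Rule | Tailored, AF not inducible or sustained | Anatomical, same patient |
|---|---|---|
| Protocol 5.3.4 | out of PP | not mentioned |
| Procedure endpoint | conversion to sinus rhythm by ablation at regions mapped in AF; not attainable as written | four-vein isolation; attainable |
| Important deviations (Protocol 10.2) | failed induction not listed; crossover listed | failed induction not listed |
| PP definition (Protocol 6.1, SAP 4.1.3) | no inducibility criterion | no inducibility criterion |
| mITT (Protocol 6.1, SAP 4.1.2) | kept | kept |

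No rule does. On the SAP text alone, the Tailored patient could be dropped under 5.3.4, dropped as a crossover, counted as Anatomical, or left in Tailored. Only the last removes the imbalance, and it conflicts with 5.3.4 and fits poorly with the treatment-received wording.

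**Step 2. The plan's own figures.** They serve only as the base for an illustration. HR = ln(0.77)/ln(0.62) = 0.547, as stated. A log-rank power calculation (Lakatos method, exponential survival, one-sided 0.025) gives 80.02% at N = 292, as stated. 292/0.78 = 374.4, against the stated 374. The documents give no share of non-inducible patients, no prognosis for them and no expected size of the PP set.

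**Step 3. Shift under no treatment effect.** Let p be AF freedom in each full arm, s the non-inducible share, and g their AF-free rate minus that of inducible patients.

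- Inducible patients have freedom p − s×g.
- Tailored PP, inducible only: p − s×g. Anatomical PP, everyone: p.
- Spurious difference: −s×g.
- With one rule for both arms: (p − s×g) − (p − s×g) = 0.

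| s (assumed) | g (assumed) | Shift −s×g | Removed from 146 evaluable |
|---|---|---|---|
| 5% | 10 points | −0.5 points | 7.3 |
| 10% | 15 points | −1.5 points | 14.6 |
| 20% | 20 points | −4.0 points | 29.2 |

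The sign follows g: a poorer prognosis favours Tailored. At s = 0 the shift is 0.

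**Step 4. A wider prognosis range.** Set p = 62% and s = 20%, and let AF freedom in the non-inducible group be q. Tailored PP freedom is (0.62 − 0.20×q)/0.80.

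- q = 82%: 57.0%, a difference of −5.0 points. HR = ln(0.570)/ln(0.62) = 1.18.
- q = 52%: 64.5%, a difference of +2.5 points. HR = ln(0.645)/ln(0.62) = 0.92.

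With 117 Tailored and 146 Anatomical patients, the approximate one-sided rejection rate in the PP set under no effect is 0.3% and 6.2% respectively, against a nominal 2.5%.

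**The case against.** The strongest reply is that a per-protocol set must drop patients who could not receive the assigned procedure. Dispersion is mapped in AF, so a Tailored patient without sustained AF cannot be treated as assigned, while an Anatomical patient without AF can. Adherence criteria already differ by arm in Protocol 10.2, and matching the exclusions changes the question asked. This explains the Tailored exclusion but does not justify leaving the comparison unbalanced. The criterion is observed before ablation, so it can be applied to both arms.

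Several further points stand.

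- PP is supportive and decides no hypothesis.
- The SAP prevails and does not repeat the exclusion, so it is unclear whether the 5.3.4 sentence still operates.
- SAP 4.2.6 already plans the primary analysis by AF presentation (spontaneous or induced). The spontaneous subgroup applies one pre-ablation criterion to both arms. The split has no category for failed induction, however.
- The share may be close to zero: enrolment requires AF, or recurrence after cardioversion, lasting at least 3 months, and antiarrhythmics are to be stopped before ablation.
- That induction applies to both arms is inferred from unrestricted wording and the contrast with the mapping heading; it is not stated outright.

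A reader might infer that the treatment-received rule moves these patients into the Anatomical PP arm. The shift would then be −2s/(1+s)×g, about 1 to 7 points under the Step 3 assumptions. The documents give this little support. The 5.3.4 sentence is specific and says they are not considered, crossovers are important deviations that lead to PP exclusion, and the fallback is ablation at the physician's discretion, which need not be the Anatomical procedure.

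**Conclusion.** The asymmetry is in the current protocol text and the SAP does not resolve it. Selection on a pre-ablation characteristic can therefore bias the supportive PP comparison for the primary endpoint and the first two secondary endpoints. The size is unknown. The 0.5 to 4 points against Tailored, compared with a planned difference of 15, rest wholly on the assumed share and prognosis gap, and neither the range nor the sign can be taken from the documents.

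Two stronger readings are tempting. A reader might infer that the primary result is compromised; it is not, because mITT retains these patients in their randomised arm. A reader might also infer that the two PP arms are bound to be different populations; they are so only if such patients exist, and the comparison is biased only if their prognosis differs. The point is worth correcting because the correction is cheap, but it does not threaten the trial's main conclusion.

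**What to change.** In SAP 4.1.3, limit the PP set in both arms to patients with spontaneous or induced sustained AF at the start of the index procedure, and state that this overrides the treatment-received rule. Align the closing sentence of the AF induction paragraph in Protocol 5.3.4. Report the number of non-inducible or non-sustained patients by arm. The change concerns the analysis set only; how such patients are treated is not at issue.

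This needs the induction outcome in both arms. Protocol Table 7 does not list it, although it refers to a fuller eCRF list that is not shown, and Table 9 schedules an AF assessment at the index procedure without restriction by arm. If the outcome is not available for Anatomical patients, report the PP comparison among patients in spontaneous AF in both arms, using the presentation variable that SAP 4.2.6 already needs. In that case, do not read the one-sided PP result as evidence of robustness.

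The cost is SAP and protocol wording and a slightly smaller Anatomical PP set, which would lose some patients who received their assigned PVI in full. If the induction outcome was captured in both arms, no new data are needed.

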### Mapping (only for Tailored group)

For the Tailored group, careful biatrial high density dispersion mapping must be performed as the first step of the procedure. A biatrial mapping shorter than 20 minutes is considered incomplete. An incomplete mapping with failure to terminate the AF is considered a deviation of the protocol (cf. X – DEVIATIONS FROM CLINICAL INVESTIGATION PLAN).

Operators must map each region of both atria carefully. Electroanatomic color maps (i.e. voltage maps with minimal interpolation area) or the density of electroanatomic dots on 3D shells can be visually used to verify that the biatrial mapping has been completed. Operators must insist in difficult areas: ridge, anterior Right Superior Pulmonary Vein, area around the transseptal puncture, CS, right septum, area between RA Appendage (RAA) and septum.

Operators should move the mapping catheter slowly and remain in each position for at least 2-3 seconds. If the upper frame of VX1 interface changes from blue to orange/red, the corresponding dipoles must be manually tagged on the 3D shells (white/golden dots respectively – cf. VX1 instructions-for-use). Accuracy and relevance of dispersion regions should be confirmed by the operator by checking EGMs visually. If VX1 identifies an area of dispersed electrograms that the operator does not agree with, this should be documented.

If a dispersion area is detected, the operator must stay and move slowly in this area: a high number of dots is required to define the precise boundaries of the dispersion area.

### Intraprocedural anticoagulation

Use of intraprocedural anticoagulation consistent with your standard practice should be used during the index ablation. It is recommended that heparin should be administered prior to or immediately following transseptal puncture during AF catheter ablation procedures and adjusted to achieve and maintain an ACT of at least 300 seconds.

### Ablation procedure in the Tailored group

In the Tailored group, the procedure endpoint is sinus rhythm conversion by ablation at dispersion regions mapped during AF and potential subsequent AT(s).

Once mapping is complete:

- 1) The operator starts by ablating all dispersion areas. Tailored-PV-encircling along dispersion regions is recommended during dispersion areas ablation (cf. Figure 2). Ablation should always be done in a manner to either cover the dispersed electrograms or encircle a large area of dispersed electrograms (cf. Figures 3 and 4)
- 2) The operator then completes the isolation of the 4 PVs
- 3) The electrical connection of the 4 PVs is checked at the end of the procedure according to each site routine practice. Additional perivenous ablation can be performed to electrically disconnect the connected PV(s).

 Tailored-PVI or Tailored-PV-encircling corresponds to PVI or PV-encircling along dispersion areas around the PVs in order to optimize the flow of the procedure.

[figure not shown]

Figure 2: Tailored-PVI after Tailored-PV-encircling

In case of failure to terminate AF after ablation of all dispersion areas, at least one re-mapping/re-ablation is mandated, and two complete re-mappings are recommended. If the patient did not convert to sinus rhythm with ablation, a DC electrical cardioversion is performed.

If sinus rhythm is restored before ablation at all dispersion areas, the completion of the ablation set is mandatory, except in the atrial regions positioned close to the esophagus, phrenic nerve, AV node and/or sinus node. This list is not exhaustive, the operator can identify and document any other potentially hazardous areas for ablation.

When a sustained AT results from the ablation of all dispersion areas, mapping and ablation of AT must be performed with the use of activation maps  $\pm$  VX1  $\pm$  pacing maneuvers.

In case of linear ablation performed for macro-reentry (roof, perimital, cavo-tricuspid isthmus (CTI) flutter), lines should be validated by establishing a post-ablation bidirectional block. The impossibility of performing the line validation must be documented. No line validation is required without documented macro-reentry.

If two ablation areas are close ( $< 2$  cm) or if one ablation area is close ( $< 2$  cm) to an electrically neutral structure (PV, valva), it is recommended to join them in order to reduce the risk of creating areas prone to AT – “Ablate & Connect” strategy (cf. Figure 3).

[figure not shown]

Figure 3: Connection of close dispersion areas (Ablation tags diameter on the 3D shells = 6 mm).

In the case of a wide and extensive dispersion area, white dots can be encircled so as to electrically isolate each dispersion zone – “Circle & connect” strategy (cf. Figure 4).

[figure not shown]

Figure 4: Centripetal ablation

The Tailored ablation protocol is summarized in Figure 5.

[figure not shown]

Figure 5: The Tailored protocol

